We propose to repeat the trial using an identical design and intervention, but including only urine collected from long term care facilities (LTCF). The control arm is standard of care. We hypothesize that the modified reporting intervention will also reduce treatment of ASB in the LTCF population, without causing harm.

Objectives

Research Question: Among patients with positive urine cultures collected from LTCF reported by Health Sciences microbiology laboratory, would restricted reporting, as compared to standard reporting, lead to a reduction in the rate of inappropriate antibiotic therapy without an increase in bacteremia or death over 30 days?

Trial design

Randomized controlled trial, 2 parallel groups with equal allocation, superiority analysis.

Methods: Participants, interventions, and outcomes

The proposed study is a randomized trial of two methods of laboratory reporting in which physicians are the main research participants. At the time of positive urine culture results, the specimen will be randomized in the laboratory using computer generated random numbers placed into serially numbered sealed, opaque envelopes, into two equal groups. One group will receive modified reporting, and the other group will receive standard reporting of bacterial identification and susceptibility. Physicians receiving modified reports will have the option to call the laboratory to receive complete results, or not. Complete results will be released by laboratory information system to physicians who call to request them. Physicians will be informed about the study prior to initiation, and debriefed about the study after the results have been collected.

The primary efficacy outcome is proportion of appropriate antibiotic therapy prescribed by physicians, based on published diagnostic criteria for ASB and UTI among catheterized patients. Appropriate therapy is defined as any treatment for UTI, or no treatment for ASB. Inappropriate therapy is defined as no treatment for UTI, or treatment for ASB. The primary safety outcome is rate of bacteremia and death. The study investigators will determine the

diagnosis based on a chart assessment to determine if the patient has UTI, CA-UTI, ASB or CA-ASB.

The definition of UTI in LTCF will be based on 2017 Canadian LTCF surveillance guidelines.(12) For residents without an indwelling catheter, criteria 1 and 2 must be present with no other identified source of infection, OR criteria 2 and 3.

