In the previous trial of the same intervention, modified reporting increased the appropriateness of treatment from 29/55 (52.7%) to 44/55 (80.0%) ($p=0.002$), for an absolute difference of +23%.(11) Accepting a risk of type 1 error of five percent, and a risk of type 2 error of twenty percent, the study will require $2N=90$ patients. To account for missing data, recruitment will be increased to 100 patients.

The microbiology laboratory receives 130 urine specimens per day, with 30 percent reported as significant growth (40 specimens per day). Ten percent are submitted from LTCF (4 positive specimens per day). In the previous trial, approximately 40% of eligible specimens were excluded based on exclusion criteria. Recruitment of 100 specimens will require approximately 40-60 days.

The statistical test to be used is a comparison of proportions between two groups (T test, two-sided analysis). Because true diagnosis may be biased by lack of access to clinical information, an intention to treat analysis including all patients randomized will be performed.

Recruitment

Every urine specimen received for culture during the study period will be assessed for inclusion.

Allocation:

Sequence generation

Randomization sequence will be generated without blocking or stratification (Research Randomizer 4.0)(13).

Allocation concealment

Reporting assignments will be placed into serially numbered, sealed, opaque envelopes.

Implementation

Allocation sequence will be generated by investigators. Investigators will enroll specimens and assign specimens to reporting interventions.

Blinding

Trial participants (physicians) will not be blinded to the intervention because the laboratory report will reveal the intervention. Investigators will be blinded to assignment. Data analyst will not be blinded to assignment.

Data collection methods

After randomization and reporting, a physician investigator will assess inpatients for the true diagnosis of UTI or ASB at two days after reporting. Health records will be accessed including demographics, symptoms, treatment decisions and outcomes.

If patients are discharged from hospital before thirty days, primary care physicians will be contacted by phone for additional clinical information. If patients die before thirty days, available data will be analyzed.

Frequency of physician calls requesting complete reporting will be recorded.

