Urine culture is reported according to laboratory protocol by licenced medical laboratory technologists, in categories of significant growth, non-significant growth, and no growth, based on quantity of growth and number of bacterial types detected. Antimicrobial susceptibility is reported according to laboratory protocol, including selected first and second-line antibiotics, as susceptible, intermediate or resistant. Drug cost and dosage suggestion are provided.

Data collection form attached.

Data management

Data collection will use a paper case report form, and entered into a trial database by a graduate student. Variables will be coded appropriately. The dataset will be protected using a

password and stored on a laptop computer during data entry. After data entry is completed, data integrity will be reviewed by a second investigator, and then the dataset will be locked for analysis.

Statistical methods

All specimens randomised and reported will be included in the Intention-to-treat (ITT) analysis. Specimens inappropriately included will be excluded from the Per-protocol (PP) analysis. The proportion of appropriate treatment will be compared using two-sided Pearson chi squared test (SPSS 23.0, IBM, USA). Adjusted analysis may be performed if appropriate. A subgroup defined as specimens in which physicians requested complete reporting will be analysed for appropriateness, compared to the standard reporting arm. Missing data will not be imputed.

Data monitoring

A data monitoring committee will not be used, as a single investigator will assume responsibility for data quality. A single interim analysis at approximately 50% recruitment will be performed, and the study stopped if the primary outcome achieves statistical significance.

Harms

Serious adverse events will be reported to the ethics committee within 24 hours. Adverse events will be collected by the investigators at day 2, day 7 and day 30. Patients with adverse events will be provided care in hospital.

Auditing

There will not be auditing of trial conduct during or after the trial.

Research ethics approval

The protocol will be submitted to the Provincial Health Research Ethics Board.

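### The half-way efficacy stop has no adjusted threshold, so testing at 5% on both looks gives a type I error of about 8-10%, not 5%

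*Combined protocol and SAP*

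**What the plan says.** - **Interim look** (Data monitoring): "A single interim analysis at approximately 50% recruitment will be performed, and the study stopped if the primary outcome achieves statistical significance". The same section says there will be no data monitoring committee.
- **Error rates** (Sample size): "Accepting a risk of type 1 error of five percent, and a risk of type 2 error of twenty percent". This is the only significance level in the document. The section arrives at 90 patients, raised to 100 for missing data.
- **Test** (Statistical methods): "The proportion of appropriate treatment will be compared using two-sided Pearson chi squared test".
- **Allocation** (Sequence generation): "Randomization sequence will be generated without blocking or stratification", so the arms may be somewhat unequal at each look.

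No section gives an interim p-value, a stopping boundary, an alpha-spending function or a reduced level for the final test.

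**The concern.** The primary outcome gets two chances to reach significance, at about 50 and about 100 specimens, and a success at the first ends the trial. Two tests at 5% on accumulating data do not make a 5% trial. The stated error rate for the primary claim is therefore not the one that the design delivers.

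Two further consequences follow from stopping at half-way on p<0.05:

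- With about 25 per arm only a large observed difference can be significant, so the effect reported after an early stop is biased upwards.
- The research question asks for benefit without more bacteremia or death over 30 days. An early stop leaves that comparison with about half the planned patients. The Implications section makes possible routine use depend on the intervention being found safe.

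**Working it through.** **Inputs.** Alpha 5% two-sided, power 80%, rates 29/55 = 52.7% and 44/55 = 80.0%, 90 patients raised to 100 (all from Sample size); 1:1 allocation (Trial design); one interim at about 50% (Data monitoring); Pearson chi-squared (Statistical methods). One assumption: significance at the interim means p<0.05.

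**1. The plan's own sample size.** With p1 = 0.527, p2 = 0.800 and p̄ = 73/110 = 0.664:

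n per arm = [1.960·√(2p̄(1−p̄)) + 0.842·√(p1(1−p1)+p2(1−p2))]² / (p2−p1)²

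= [1.960·√0.4464 + 0.842·√0.4093]² / 0.2727² = 45.9, so 46 per arm and 92 in total.

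The unpooled version, (1.960+0.842)²·0.4093/0.2727² = 43.2, gives 44 per arm and 88 in total. The stated 90 lies between the two. It is a fixed, single-look design with nothing set aside for an interim test.

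**2. Two looks, normal theory.** The interim and final z-statistics have correlation √0.5 = 0.707. Under the null hypothesis:

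overall error = 1 − P(|Z1|<1.96 and |Z2|<1.96) = 1 − 0.9169 = **8.3%**.

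It is 8.6% with the look at 40% and 8.0% with the look at 60%.

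**3. Two looks, exact.** Binomial enumeration of the uncorrected Pearson test, 25 then 50 per arm, equal true rates in both arms:

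| Common rate | Significant at interim | p<0.05 at both looks | Single look, 50 per arm | O'Brien-Fleming |
|---|---|---|---|---|
| 0.50 | 6.5% | 10.0% | 5.7% | 5.9% |
| 0.60 | 6.0% | 9.3% | 5.2% | 5.5% |
| 0.66 | 5.5% | 8.7% | 4.9% | 5.1% |
| 0.70 | 5.4% | 8.6% | 5.0% | 5.2% |
| 0.80 | 5.5% | 8.9% | 5.2% | 5.1% |

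With 22 or 23 then 45 per arm (the 90 before the missing-data allowance) the two-look error is 7.9-8.9%. Simulating unblocked randomization at 50 then 100 specimens gives 8.5-9.2%.

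**4. How often the rule operates, and the bias.** At 52.7% against 80.0% with 25 per arm, the exact probability of p<0.05 at the interim is 56%. For a control rate near one half the smallest significant difference is 28 points. For example, 12/25 against 19/25 gives z = 0.28/√(0.62·0.38·2/25) = 2.04, while 12/25 against 18/25 gives z = 0.24/√(0.60·0.40·2/25) = 1.73. Among trials that stop at the interim the mean observed difference is 36 points; the true difference is 27.

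**5. Boundaries that hold 5% by normal theory, with the look at 50%.**

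- O'Brien-Fleming: |z|≥2.797 (p<0.0052) at the interim, |z|≥1.977 (p<0.048) at the end.
- Pocock: p<0.0294 at each look.
- Haybittle-Peto (p<0.001, then 0.05): overall error 5.02%.

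Exact power at the design rates and 50 per arm is 83.5% for a single look, 83.7% for O'Brien-Fleming and 85.5% for p<0.05 at both looks. At 45 per arm it is 80.5% for a single look and 79.5% for O'Brien-Fleming. To keep 80% power by normal theory, the maximum of 90 becomes 90 × 1.008 = 91 for O'Brien-Fleming and 90 × 1.110 = 100 for Pocock.

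**The case against.** The strongest objection is that the protocol never says what significance means at the interim. A stricter level could have been intended, and then the inflation does not follow. That is right as logic, but 5% is the only level in the document and nothing points to another. If a stricter one was meant, it and the matching final level still have to be written down before interim data are seen. The data analyst is unblinded and there is no monitoring committee, so an undefined threshold has no other safeguard.

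Other points stand in part:

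- The 10% end is not all due to the second look. At a common rate of 0.50 the single-look Pearson test already runs at 5.7% because the data are discrete. The best single figure is 8.3%.
- For the same reason O'Brien-Fleming gives exactly 5% only by normal theory. Its exact error is 5.1-5.9%, against 4.9-5.7% for a single look. It removes nearly all of the repeated-testing excess, not the discreteness.
- The correction is not strictly free. The apparent gain of 83.7% over 83.5% is a discreteness effect, and at 45 per arm O'Brien-Fleming loses about 1 point.
- The trial is not sized for death or bacteremia even at 50 per arm, so the loss of safety information is a secondary argument.
- Any efficacy stop overstates the effect in the trials that stop; a strict boundary makes such stops rarer but does not remove the bias.

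None of this changes the conclusion.

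**Conclusion.** The concern holds. Followed as written, with 5% at both looks, the plan has a two-sided type I error of 8.3% by normal theory and 8.6-10.0% exactly for 25 then 50 per arm, against a stated 5%. The result rests on reading significance as p<0.05 at each look and on an interim near half-way; moving the look between 40% and 60% changes the normal-theory figure only from 8.6% to 8.0%. Two other inconsistencies do not affect it: the Sample size section prints a difference of +23% where its own rates give 80.0 − 52.7 = 27.3 points, and it names a T test where Statistical methods names chi-squared. This should be corrected before the interim analysis, because a threshold chosen after the data are seen cannot restore the error rate.

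**What to change.** State the rule in Data monitoring and repeat the final level in Statistical methods. One suitable form is a two-look O'Brien-Fleming boundary: stop at the interim only if |z|≥2.797 (two-sided p<0.0052), otherwise test at the end with |z|≥1.977 (p<0.048). If the look does not fall at half-way, recompute the thresholds for the actual fraction.

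Haybittle-Peto (p<0.001, then 0.05) is also acceptable and simpler. The choice affects how often the trial stops early under the design rates: 22% with O'Brien-Fleming and 9% with Haybittle-Peto, against 56% with p<0.05.

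The other sound option is to drop the efficacy stop. Full recruitment is expected to take 40-60 days, so stopping half-way saves only about 20-30 days of recruitment, and completing it keeps the full safety sample.

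The cost is one sentence. With 100 recruited, no further specimens are needed and power stays close to or above 80%.

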elderly with high care needs. One centralized microbiology laboratory performs all testing for the city.

Inclusion and exclusion criteria for participants

Consecutive positive urine cultures collected from patients admitted to LTCF will be included. All methods of urine collection will be included (midstream, in-and-out catheterization, indwelling catheter). Exclusion criteria will be urine cultures not collected from LTCF patients, pregnancy, antibiotic treatment at the time of collection, and patients known to have blood neutrophils <1.0 within 7 days.

Interventions

The modified report states “This POSITIVE urine culture may represent asymptomatic bacteriuria or urinary tract infection. If urinary tract infection is suspected clinically, please call the microbiology laboratory at [name] between 0900 to 2300, or the microbiology technologist on-call at [name] at night, for identification and susceptibility results.” The standard report provides bacterial count, bacterial identification and bacterial susceptibility results.

The report is provided to the physician approximately 24 hours after receipt of the specimen, when cultures have been examined after overnight incubation. The intervention is a single report, so it is not possible to discontinue the intervention, or change allocation during the trial. There will no other influence on concomitant care or treatment.

Outcomes

Primary efficacy outcome:

Proportion of appropriate antibiotic therapy prescribed by physicians. Appropriateness is determined by investigators based on chart review, based on diagnosis of UTI or ASB. Appropriateness is determined within two days from positive urine culture.

Secondary efficacy outcomes:

Proportion of calls from physicians requesting complete report

Primary safety outcomes:

Mortality rate over thirty days from positive urine culture.

Bacteremia rate over thirty days from positive urine culture.

Adverse event rate over seven days from positive urine culture.

Participant timeline

TIMEPOINT	STUDY PERIOD				
	Enrolment	Allocation	Post-allocation		
	Day -1	Day 0	Day 2	Day 7	Day 30
ENROLMENT:					
Eligibility screen	Urine specimen received at microbiology laboratory	Urine culture result reported to physician	Physician treatment decision made	Safety assessment	Safety assessment
Allocation	X				
INTERVENTIONS:					
Reporting		X			
ASSESSMENTS:					
Appropriateness			X		
Adverse Events			X	X	X
Bacteremia			X	X	X
Mortality			X	X	X

Sample size

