Physician consent requirement will be requested to be waived because the intervention poses no more than minimal risk to participants. Patient consent requirement will be requested to be waived because physicians were the research subjects. A letter will be sent to all inpatient physicians informing them about the study prior to recruitment, and a debrief meeting, offering an opportunity to withdraw physician participation, will be provided.

The benefit of this study to patients includes a reduction in adverse events caused by inappropriate antibiotic treatment. The risk to patients includes possible untreated UTI. The benefit to physicians includes education toward appropriate treatment of ASB. The risk to physicians includes additional effort to access laboratory results for UTI.

Protocol amendments

Protocol amendments will be submitted to the ethics committee and trial registry and informed to investigators.

Consent or assent

Not applicable.

Confidentiality

Identification of patients will be required during data collection, but will be removed from trial dataset before analysis. No identifiers will be included in reporting of results.

Declaration of interests

The investigators and sponsor hold no financial interests in the trial.

Access to data

The trial dataset and protocol will be accessible to the investigators during the trial, and made publically available after the analysis is completed.

Ancillary and post-trial care

There will be no post-trial care provided.

Dissemination policy

Investigators will communicate trial results via unrestricted publication. All investigators are eligible for authorship, according to contribution.

Biological specimens

There will be no collection, testing or storage of biological specimens for genetic or molecular analysis.

Budget

The only expense of the project will be the graduate student to collect the data, perform the analysis and write the manuscript.

Implications

A reduction in inappropriate antibiotic treatment may reduce complications of treatment such as diarrhea due to *Clostridium difficile*, selection of bacteria towards drug resistance, and cost of treatment. If the intervention is determined to be safe, it may be considered for implementation in routine laboratory practice. The results will generalize to adult inpatients in Canada and around the world.

References

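### The interim rule can stop the trial on the day-2 efficacy result alone, with few 30-day follow-ups complete, and would then halve the final sample for bacteremia and death

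*Combined protocol and SAP*

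**What the plan says.** The research question (Objectives) has two parts. It asks whether modified reporting would "lead to a reduction in the rate of inappropriate antibiotic therapy without an increase in bacteremia or death over 30 days".

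The two parts are measured on different clocks. For efficacy, the Outcomes section says: "Appropriateness is determined within two days from positive urine culture". The primary safety outcomes there include "Mortality rate over thirty days from positive urine culture" and "Bacteremia rate over thirty days from positive urine culture", together with adverse events over seven days. The participant timeline places safety assessments at days 2, 7 and 30.

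On size and pace, the Sample size section derives 2N=90 from appropriateness alone, then says: "To account for missing data, recruitment will be increased to 100 patients". It adds: "Recruitment of 100 specimens will require approximately 40-60 days".

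The only stopping rule is in Data monitoring: "A single interim analysis at approximately 50% recruitment will be performed, and the study stopped if the primary outcome achieves statistical significance". The same section says there will be no data monitoring committee. Harms provides for serious adverse events to reach the ethics committee within 24 hours, but does not connect this to the interim decision. Implications makes adoption conditional on safety: "If the intervention is determined to be safe, it may be considered for implementation in routine laboratory practice".

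**The concern.** The stopping rule answers only one half of the research question. It refers to the primary outcome in the singular. Although the plan also lists primary safety outcomes, appropriateness is the only outcome given a statistical test, so it is the natural referent. That outcome is available two days after the report and bacteremia and death need 30 days, so the decision comes before most of the 30-day information exists.

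The rule also sets the two aims against each other. The better the modified report works on prescribing, the more likely the trial is to end with half its planned safety sample. The plan itself names untreated UTI as the risk to patients. The previous trial, which is the basis for expecting safety, followed patients for seven days and excluded those with indwelling catheters. Thirty-day data in long term care residents are therefore a large part of what this trial adds.

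The point is separate from the choice of interim significance level. A stricter level makes the stop less likely but does not change what is lost when it happens.

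**Working it through.** **Inputs.** From Sample size: 100 specimens in 40-60 days; 4 positive long term care specimens per day, about 40% excluded; planning rates 29/55 (52.7%) and 80.0%; two-sided 5% error; 80% power. From Outcomes: day 2 for efficacy, day 30 for bacteremia and death. From Background: 2/55 deaths and 2/55 bacteremias with modified reporting over 7 days. Uniform accrual and a prompt interim analysis are assumed.

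**Reproducing the plan's figures.** The two-proportion formula with pooled variance under the null gives, per arm, [1.96 × √(2 × 0.6635 × 0.3365) + 0.842 × √(0.527 × 0.473 + 0.80 × 0.20)]² / 0.273² = 45.8, so 46 per arm and 92 in total, close to the stated 90. Recruitment time is 100 / (4 × 0.6) = 41.7 days, inside the stated 40-60.

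**When the look happens.** The rate is 100/40 = 2.5 to 100/60 = 1.67 specimens per day. The 50th specimen arrives at day 20-30 and its day-2 outcome is known at day 22-32.

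**Follow-up available at the look.**

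| | 40-day recruitment | 60-day recruitment |
|---|---|---|
| Day of look | 22 | 32 |
| Past day 30, of 50 | 0 | (32 − 30) × 1.67 = 3.3, so about 3 |
| Past day 7, of 50 | (22 − 7) × 2.5 = 37.5, so 37 | (32 − 7) × 1.67 = 41.7, so 41 |
| Share of the 50 specimens' 30-day person-time observed | about 39% | about 56% |

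If the look came a week after the 50th specimen under the slow rate, (37 − 30) × 1.67 = 11.7, so about 12, would be past day 30.

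**Chance of stopping.** Exact enumeration of the two-sided Pearson chi-squared test with 25 per arm, at true rates 29/55 and 0.80:
- p<0.05: 0.56
- strict level of about 0.005: 0.22

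**Final safety sample after a stop.** About 50 specimens, or up to 50 + 2 × 2.5 = 55 if enrolment runs on during the two-day lag, against 100 planned.
- Upper limit with zero events in an arm, one-sided 95%: 1 − 0.05^(1/25) = 11.3% with 25; 1 − 0.05^(1/50) = 5.8% with 50.
- 95% half-width for the difference, 1.96 × √(2p(1 − p)/n), with p = 2/55 = 3.6% in both arms (an assumption, borrowed from a 7-day rate in acute care): 10.4 points with 25 per arm; 7.3 points with 50 per arm.

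**What full recruitment can and cannot do.** Power of the same test to detect a doubling, with assumed base rates:

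| Rates | 25 per arm | 50 per arm |
|---|---|---|
| 5% to 10% | 0.08 | 0.14 |
| 10% to 20% | 0.17 | 0.30 |

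**The case against.** Four things can be said for the rule as written.

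1. *The look is not blind to safety.* A reader might infer that the decision would be taken with no safety information. The documents do not support that. Deaths and bacteremias are also assessed at days 2 and 7; 37-41 of 50 would have passed day 7, the horizon of the previous trial; and serious adverse events are reported within 24 hours. What stands is that few 30-day follow-ups are complete and that the stopping rule uses none of this information.

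2. *A stop loses no follow-up.* A reader might infer that those already randomised would drop out of the safety analysis. Nothing cancels their day-30 assessment, and the report is a single act. After a stop, about 50 specimens could still have full 30-day data. Continued follow-up is not stated for that case, but the real loss is in the number finally analysed.

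3. *Fifty per arm is also too few.* A reader might infer that completing recruitment secures the safety conclusion. It does not: the trial was sized on appropriateness only, no safety margin or safety test is given, and power for a doubling is low at either size. The zero-event limit also flatters the contrast, since the previous trial saw deaths and bacteremias within seven days. This objection stands in full as a limit on the remedy. It is not a reason to give up half of an already small sample.

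4. *Stopping a superiority trial for efficacy is legitimate.* So it is in general, and a narrower change, requiring a by-arm review of deaths and bacteremias before stopping, would meet part of the timing concern. It would not restore the safety sample, and here the stop saves only 20-30 days.

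**Conclusion.** The concern holds in limited form. The plan allows the trial to end on the day-2 efficacy outcome, with no safety condition, when 0 to about 3 of 50 specimens have completed 30 days. A stop halves the final safety sample, widening the 95% interval for the difference from about ±7.3 to ±10.4 points at an assumed 3.6% event rate in each arm. If the planning effect is true and 0.05 is used at the look, a stop is more likely than not (0.56); at a strict level it remains a realistic possibility (0.22).

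The timing rests on uniform accrual at the plan's own rate and a prompt analysis. The halving needs neither: it follows from stopping at about half recruitment.

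The change is worth making before recruitment starts. The trial could run without it, but the rule weakens one half of the stated objective for little gain.

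**What to change.** In Data monitoring, delete the stop for efficacy and state that the planned 100 specimens will be recruited whatever the interim efficacy result. If a mid-trial look is kept, define it as a review of deaths, bacteremias and serious adverse events by arm, with no efficacy claim. State in Data collection methods that every randomised specimen is followed to day 30.

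In Statistical methods, add that bacteremia and death over 30 days will be reported by arm as an estimated difference with its 95% confidence interval, and that a non-significant difference will not be read as showing no increase.

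Cost: a few sentences of text, up to 20-30 more days of recruitment within the planned 40-60, and no chance of finishing early. No enlargement beyond the planned size is needed. The change limits the loss of safety information; it does not make the trial adequate for rare events.
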